5.14. Other Considerations for Data Analyses and Data Handling Conventions

Other considerations for data analyses and data handling conventions are outlined in the appendices:

| Section | Component |
|---------|--|
| 15.3 | Appendix 3: Assessment Windows |
| 15.4 | Appendix 4: Study Phases and Treatment Emergent Adverse Events |
| 15.5 | Appendix 5: Data Display Standards & Handling Conventions |
| 15.6 | Appendix 6: Derived and Transformed Data |
| 15.7 | Appendix 7: Reporting Standards for Missing Data |
| 15.8 | Appendix 8: Laboratory Parameters and Toxicity Grades |
| 15.9 | Appendix 9: Biomarkers |

6. STUDY POPULATION ANALYSES

6.1. Overview of Planned Study Population Analyses

The study population analyses will be based on the Intent-to-Treat population, unless otherwise specified.

Study population analyses including analyses of subject's disposition, protocol deviations, demographic and baseline characteristics, prior and concomitant medications, and exposure and treatment compliance will be based on GSK Core Data Standards. See Study Population shells for mock displays.

6.2. Disposition of Subjects

The number and percentage of subjects randomized by country and site will be summarized overall and by treatment group using the Randomized population [T11.01].

The number of subjects in each population for the primary analyses (Screened, Randomized, ITT, MITT, MITT Week 52 prior to COVID-19, MITT Week 64 prior to COVID-19, Per Protocol, Ongoing at Week 52, Ongoing on study treatment at Week 52, As Treated and PK) and for the end-of-study analysis (Ongoing at Week 64, Ongoing on study treatment at Week 64, and Completed) will be summarized overall and by treatment group [T11.02, T21.01]. A summary of the reasons for the screen failures will be provided along with a listing of the subjects who were screen failures [T11.03, L11.01]. If there are any subjects who are randomized but do not receive any study treatment, they will be included on the subject disposition listing in the Randomized population, but not the ITT population.

Subject status through Week 52 (Year 1), and over the entire study (Years 1&2 Combined) will be summarized for the ITT [T11.04, T21.02] and MITT [T11.05, T21.03] populations.

For the ITT population, a summary of treatment status and reasons for discontinuation of study treatment will be produced at Week 52 and at end of study. The number and percentage of subjects who completed the study treatment as planned as well as subjects who stopped study treatment prematurely, including reasons for treatment discontinuation, will be displayed by treatment group [T11.08, T11.09, T21.04].

The cumulative number and percentage of subjects withdrawing from the study by visit will be summarized for the ITT (T11.07) population at Week 52, and at Week 104 (T21.05) and listed (L11.03, L21.02).

A Kaplan-Meier (KM) plot of time to study withdrawal will be generated to evaluate the pattern of study withdrawals/LTFU/death over time up to Week 52 [F11.01].

Subjects who withdraw (including LTFU and death) will be considered to have experienced an event (cens=0) at:

Time to study withdrawal = withdrawal date – 1st Belimumab injection date + 1

Subjects ongoing at Week 52 will be considered censored (cens=1) at:

Time to study withdrawal = Week 52 date – 1st Belimumab injection date + 1

The figure will be repeated for the Week 104 reporting with all data from Year 1 and 2 [F21.01].

Subjects completing at Week 104 will be considered censored (cens=1) at:

Time to study withdrawal = Week 104 date – 1st Belimumab injection date + 1

For the ITT population, the subject's study completion status will be assessed to evaluate percentages of study withdrawals by treatment group as well as the reasons for study withdrawal. The number and percentage of subjects who completed through Week 52 (Week 64 and 104) and who withdrew from the study, including reasons for withdrawal, will be displayed by treatment group and overall for Year 1 and Year 1&2 separately [T11.06, T21.06]. A listing of subjects who withdrew from the study, including reason for and time to study withdrawal will also be provided. [L11.03, L21.02].

Additionally, the cumulative number and percentage of subjects who prematurely discontinued from the planned study treatment by visit will be displayed by treatment group and overall for Year 1 and 2 separately for the ITT and MITT populations [T11.10, T11.11, T21.07, T21.08].

A listing of subject disposition will be provided showing their completion status and whether they are included in each population [L11.02, L21.01].

A shift table that summarizes the differences between the levels of each stratification factor at screening compared to values used in randomization will be provided [T11.16].

The COVID-19 environment onset and end dates will be listed (L11.15, L21.09).

Current COVID-19 environment onset dates are shown in Section [15.6.16](#)

6.3. Demographic and Baseline Characteristics

Continuous parameters will be summarized using descriptive statistics (mean, standard deviation, median, 25th percentile, 75th percentile, minimum, and maximum). Categorical parameters will be summarized using counts and percentages.

Demographic and baseline characteristics, as well as stratification factors, will be listed for all patients [L11.08, L11.09].

The following Demographic and baseline disease activity indicators will be summarized:

| PARAMETER | SUMMARY TYPE |
|--|--|
| Medical History | |
| Past Medical Conditions [T11.22]. and Current Medical Conditions [T11.23]. | Categorical: presented if past [current]. medical history is present |
| Family History of Cardiovascular Risk Factors [T11.24]. | Categorical: Yes, No |
| Stratification Factors at Randomization [T11.25] | |
| SLEDAI-2K (PI) | Categorical: <=9, >=10 |
| Baseline immunosuppressant use | Categorical: 
 - Use - Non-use |
| Corticosteroid dose (prednisone equivalent) | Categorical: 
 - ≤10 mg/day - >10 mg/day |
| Demographic [T11.17, T11.18 (MITT population), T11.19] | |
| Age (years) | Continuous Categorical: 
 - ≤45 years, - >45 – <65 years - ≥65 years 
 ○ ≥65 – <75 years ○ ≥75 years |
| Country Region | USA/Canada, Europe, Rest Of World (Section 5.5.2) |
| Country | As observed |
| Corticosteroid dose (prednisone equivalent) | Categorical: 
 - ≤5 mg/day - >5 mg/day |
| Corticosteroid dose (prednisone equivalent) | Categorical: 
 - 0 mg/day - >0 mg/day |
| Height (cm) | Continuous |
| Weight (kg) | Continuous |
| Body Mass Index (BMI) (kg/m ²) | Continuous |
| Blood Pressure [T11.21]. | Continuous |
| Heart Rate (beats/min) [T11.21]. | Continuous |
| Sex | Categorical: Female, Male |
| Ethnicity: Hispanic or Latino origin | Categorical: Hispanic or Latino origin, Not Hispanic or Latino origin |
| Race and Racial Combination Details [T11.20]. | Categorical: White/Caucasian, Asian, African American/African Heritage, Alaskan Native or American Indian, Native Hawaiian or Other Pacific Islander, and Multiracial |

| PARAMETER | SUMMARY TYPE |
|---|--|
| Baseline Disease Activity | |
| SLEDAI-2K score (IBA) [T11.26, T11.27 (MITT)]. | Continuous Categorical: <=9, 10-11, >=12 |
| SLEDAI-2K score (PI) [T11.26, T11.27 (MITT)]. | Continuous Categorical: <=9, 10-11, >=12 |
| PGA score [T11.26, T11.27 (MITT)]. | Continuous Categorical: 0-1, >1 – 2.5, >2.5 |
| SLICC/ACR Damage Index score [T11.26, T11.27 (MITT)]. | Continuous Categorical: 0, 1, >1 |
| SLE disease duration (years) [T11.26, T11.27 (MITT)]. | Continuous |
| SLEDAI-2K (PI) by organ domain and item at baseline [T11.29]. | Categorical: presented if Yes |
| Baseline immunoglobulin levels (g/L): IgA, IgG, and IgM [T11.30]. | Continuous value Categorical: - IgA: <LLN (0.81 g/L), >ULN (4.63 g/L) - IgG: <LLN (6.94 g/L), >ULN (16.18 g/L) - IgM: <LLN (0.48 g/L), >ULN (2.71 g/L) |
| Baseline levels of complement: C3 [mg/dL] [T11.26, T11.27 (MITT)]. | Continuous Categorical: high (>180 mg/dL), normal (90 - 180 mg/dL), low (<90 mg/dL) |
| Baseline levels of complement: C4 [mg/dL] [T11.26, T11.27 (MITT)]. | Continuous Categorical: high (>40 mg/dL), normal (10 - 40 mg/dL), low (<10 mg/dL) |
| Complement Level [T11.26, T11.27 (MITT)] | Categorical: At least one low C3/C4, No low C3/C4 |
| Anti-dsDNA [IU/mL] [T11.26, T11.27 (MITT)]. | Continuous Categorical: -positive (≥ 30 IU/mL) -negative (< 30 IU/mL) |
| Complement Level and anti-dsDNA Level [T11.26, T11.27 (MITT)]. | Categorical: At least one low C3/C4 and anti-dsDNA ≥ 30 IU/mL; Not (At least one low C3/C4 and anti-dsDNA ≥ 30 IU/mL) |
| Proteinuria (g/24h) [T11.26, T11.27 (MITT)] | Continuous value Categorical: <=0.5 >0.5-<1 1-<2 >=2 |

| PARAMETER | SUMMARY TYPE |
|--|--|
| Baseline autoantibody levels [T11.31]. | |
| ANA [Titer]. | Continuous Categorical: -positive (≥ 80 Titer) -negative (< 80 Titer) |
| anti-cardiolipin (aCL) | Continuous for each of aCL-IgA, aCL-IgG, aCL-IgM Categorical (Positive is ≥ 15) : -positive (if any of the three isotypes aCL-IgG, aCL-IgA or aCL-IgM are above the upper limit of normal) -negative (if at least one is non-missing and none of the isotypes above the limit of quantification) -missing (all three isotypes are missing) |
| anti-dsDNA and/or ANA positive | Categorical: Yes, No |
| Beta-2-glycoprotein [U/mL]. for each of the isotypes IgG, IgA, and IgM | Continuous Categorical: Positive (≥ 21 U/mL), Negative |
| Lupus anticoagulant | Continuous |
| RNA Interferon Signature [T21.16] | Continuous Categorical: Low, High |
| B cells and T-cells at Baseline [T11.32] | |
| CD19+ Total B cells (cells/mL) B cells CD20+ (cells/mL) B cells CD20+ (%) Naive B cells IgD+ (cells/mL) Naive B cells IgD+ (%) Naive CD20+ CD27- (cells/mL) Naive CD20+ CD27- (%) Activated Total B cells CD95+ (cells/mL) Activated Total B cells CD95+ (%) Memory CD20+ CD27+ (cells/mL) Memory CD20+ CD27+ (%) Non-switched memory CD27+ IgD+ (cells/mL) Non-switched memory CD27+ IgD+ (%) Switched memory CD27+ IgD- (cells/mL) Switched memory CD27+ IgD- (%) Plasmablasts CD27b CD38b (cells/mL) Plasmablasts CD27b CD38b (%) Plasmablasts CD20+ CD27b CD38b (cells/mL) Plasmablasts CD20+ CD27b CD38b (%) Plasmablasts CD20- CD27b CD38b (cells/mL) Plasmablasts CD20- CD27b CD38b (%) | Continuous |

| PARAMETER | SUMMARY TYPE |
|--|--|
| Transitional CD10+ CD24b CD27- CD38b (cells/mL) Transitional CD10+ CD24b CD27- CD38b (%) Transitional CD24b CD27- CD38b (cells/mL) Transitional CD24b CD27- CD38b (%) CD3+ Total T cells (/uL) CD8+ T cells (/uL) CD4+ T cells (/uL) | |
| BLyS (free) [ng/mL] . | Continuous Categorical: below limit of quantification [LOQ]. (<0.05 ng/mL), above LOQ; <75 th percentile, >=75 th percentile |
| Columbia Suicide Severity Rating Scale (C-SSRS) at Baseline [T11.33]. | |
| C-SSRS responses by behavior and ideation components for lifetime and over the last six months | Categorical: -Ideation: categories 1-5 with corresponding text -Behavior: categories 6-10 with corresponding text -Self-injurious behavior, no suicidal attempt |
| Patient Reported Outcomes (PROs) [T11.28] | |
| Patient Global Assessment (PtGA) | Continuous |
| Baseline FACIT-Fatigue scale score | Continuous Categorical: (<20; 20-<35; ≥35) |
| LupusQoL | Continuous |
| WPAI: Lupus | Continuous |
| Allowable SLE Medication Usage at Baseline [T11.34] | |
| Allowable SLE medications by class and drug | Categorical: Steroids, Anti-malarials, Immunosuppressants, Aspirin, NSAIDs |
| Average daily prednisone dose (mg/day) at baseline | Continuous Categorical: (0, >0 - ≤5, >5) |
| Steroid, Anti-malarial and Immunosuppressant Use at Baseline | Categorical: -Steroid Only -Immunosuppressant Only -Anti-malarial Only -Steroid and Immunosuppressant Only -Steroid and Anti-malarial Only -Immunosuppressant and Anti-malarial Only -Steroid and Immunosuppressant and Anti-malarial |

Listings will be provided for current and past medical conditions [L11.10, L21.05].

The summary of demographic and baseline characteristics, baseline disease activity and allowable SLE medication will be repeated for the following subgroups:

- Age (<65 years, ≥65 years) [T11.40, T11.41, T11.42]
- Race (Black vs. Non-Black) [T11.43, T11.44, T11.45]
- Baseline SLEDAI-2K score (≤ 9 vs. ≥ 10) [T11.46, T11.47, T11.48]
- Baseline Immunosuppressant use (use vs. non-use) [T11.49, T11.50, T11.51]
- Baseline corticosteroid dose (prednisone equivalent ≤10 mg/day vs. >10 mg/day) [T11.52, T11.53, T11.54]
- Gender (Male vs Female) [T11.55, T11.56, T11.57]
- Country Region (USA/Canada, Europe, Rest of World) [T11.58, T11.59, T11.60]
- Baseline complement level (At least one low C3/C4 vs. No low C3/C4) [T11.61, T11.62, T11.63]
- Anti-dsDNA (≥ 30 IU/mL vs < 30 IU/mL) [T11.64, T11.65, T11.66]
- Baseline C3/C4 levels & anti-dsDNA (At least one low C3/C4 & anti-dsDNA ≥30 IU/mL vs. Not (At least one low C3/C4 & anti-dsDNA ≥ 30 IU/mL)) [T11.67, T11.68, T11.69]
- Baseline BLyS Protein (≥75th Percentile vs <75th Percentile) [T11.70, T11.71, T11.72]
- RNA Interferon Signature (Low vs. High) [T21.17, T21.18, TT21.19]

6.4. Concomitant Medications

Concomitant medications will be coded according to drug name as defined in the GSK Drug Dictionary, and classified according to the GSK-Drug ATC classification level 1 and ATC level 4. Concomitant medications are defined as medications that start on or before the first dose date of study treatment and end on or after the first dose date of study treatment, or medications that start after the first dose date of study treatment (see Section 15.4.1 for further details). Note that medications with partial or missing start and/or stop dates will be assumed to be concomitant unless there is evidence through comparison of partial dates to suggest otherwise, for example if the day is missing, then the month and year will be compared to the month and year of the first dose date of study treatment and if the month and year are the same or later, then the medication will be considered concomitant (see Section 15.7.2.1 for further details).

A summary of the number and percentage of subjects with concomitant medications by ATC level 1 term and ATC level 4 term will be displayed for both Year 1 and Year 2 separately [T11.35, T21.11]. A further summary of concomitant medications by ATC level 4 term and preferred term will be provided for both Year 1 and Year 2 [T11.36, T21.12]. A listing of all concomitant medication data will be displayed by treatment and subject [L11.11, L21.06].

Protocol-prohibited medication and allowable medication that results in treatment failure designation (see Section 7.7 of the protocol) will be summarized by treatment group. [T11.37, T21.13].

A listing of protocol-prohibited medication and allowable medication that result in treatment failure designation will be displayed by treatment and subject [L11.12, L21.07].

6.5. Extent of Exposure to Study Treatment

Exposure listings detail the amount of planned study medication that was taken, and re-start medication (belimumab taken in Year 2 for Arms A and B). However they do not include concomitant medication of non-study belimumab or rituximab.

Exposure data for both belimumab and rituximab will be listed for:

- Year 1: Arm A, B, and C for belimumab; and Arms A and B for rituximab/placebo in Year 1 [L11.13].
- Year 2: Arm A&B: Includes late Year 1 doses (taken in year 2) for Belimumab and re-start Belimumab; Arm C belimumab in Year 2 [L21.08].

See Section 15.6.2 for further details.

Belimumab

The extent of exposure to belimumab through Week 52 for Arm A and Arm B and through Week 104 for Arm C will be assessed by examining the duration of exposure to belimumab in days and the total number of injections a subject receives. Duration of exposure in days will be calculated as:

Duration of exposure (days) = (Last injection date – First injection date + 7).

Only complete dates will be used when calculating duration of exposure. First and last injection dates will be used, regardless of any missed doses.

Percent compliance will be calculated as:

$100 * (\text{Number of injections prescribed} - \text{Number of injections missed}) / \text{Number of injections prescribed}$.

The duration of exposure, the total number of injections, and the percent compliance will be summarized using descriptive statistics for the treatment phase. The total number of injections will also be summarized using counts and percentages using the following categories: 1 – 12 doses, 13 – 24 doses, 25 – 36 doses, 37 - 52 and > 52 doses (if applicable). [T11.38]. Similarly, exposure to belimumab in Arm C from Baseline to Week 104 will also be summarized using the following categories: 1 – 12 doses, 13 – 24 doses, 25 – 36 doses, 37 - 52 doses, 53 - 64 doses, 65 - 76 doses, 77 – 88 doses, 89 - 104 doses, and >104 doses (if applicable) [T21.14].

Exposure to belimumab will also be summarized for subjects during Year 2 only. For subjects in Arms A and B this will include incorrectly taken Year 1 medication after

Week 52 and re-start medication [T21.15]. The first dose in Year 2 will be the 1st dose the subject took on the day of or after the Week 52 visit date.

Duration of exposure (days) = (Last injection date – First injection date + 7).

Rituximab

For subjects randomized to Arms A and B, the extent of exposure to rituximab/rituximab-placebo will be assessed by examining the dose intensity and the total number of infusions, i.e. 0, 1 or 2. Dose intensity in mg will be calculated as the cumulative actual dose divided by 2. If the total volume of an infusion is not administered, the actual dose infused for that visit will be calculated as:

Actual Dose infused (mg) = Planned Dose (mg) * Percentage of volume infused

Dose intensity and total number of infusions will be summarized using descriptive statistics [T11.39].

Data Listings

Subjects for whom the treatment blind was broken [L11.14], or potentially the treatment blind broken (29 subjects inappropriately identified on a lab report) will be provided [L11.02].

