7.7.4. Additional SLE Therapy

In the 52-week, double-blind treatment phase, participants in Arms A or B who fail to adequately respond to study treatment or in the medical judgment of the investigator

cannot meet the corticosteroid taper rules, tolerate immunosuppressant withdrawal at Week 4, or who will require additional therapy will be considered treatment failures. Participants who are treatment failures will be encouraged to remain in the study and receive all safety and efficacy assessments through Week 104. At the discretion of the investigator, the participant may continue to receive belimumab SC 200 mg/week. If additional medical treatment is necessary it will also be at the discretion of the investigator and may include corticosteroids and/or immunosuppressants.

In the 52-week observational phase (Weeks 53 to 104), participants in Arms A and B may continue or reinitiate open-label belimumab SC 200 mg weekly treatment if (a) they responded clinically in the 52-week treatment phase of the study but did not meet the primary efficacy endpoint, or (b) responded clinically but subsequently experienced an increase in disease activity requiring treatment. If a participant requires rescue therapy in addition to the re-initiation of treatment with belimumab, corticosteroids >5 mg/day of a prednisone equivalent and/or immunosuppressants may be given at the discretion of the investigator. Reason for rescue therapy and medication dosing requirements should be documented in source records. Treatment with open-label rituximab is allowed, but not encouraged. Belimumab will be provided by the study, but other SLE treatments, including rituximab, will not be provided by the sponsor. In these situations the participants in Arms A or B would be considered treatment failures for the efficacy endpoints. Participants who are declared treatment failures will be encouraged to remain in the study and continue to receive all safety and efficacy assessments. Additional information on management of participants who receive open-label belimumab and/or rituximab, including the schedule for obtaining immunogenicity samples, is provided in the SRM.

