2.1.1. Study Population Tables

| Study Population Tables | | | | |
|--------------------------------|-------------------|------------|--|---|
| New output number | Old output number | Population | Title | Major modifications since original RAP |
| Subject Disposition | | | | |
| 21.01. | 21.01 | Screened | Study Populations (Year 1&2) | |
| 21.02. | 21.02 | ITT | Subject Status (Year 1&2) | |
| 21.03. | 21.04 | ITT | Subject Status and Reason for Study Withdrawal (Year 1&2) | |
| 21.04. | 21.05 | ITT | Time to Withdrawal from the Study (Year 1&2) | |
| 21.05. | 21.06 | ITT | Treatment Status and Reasons for Discontinuing Belimumab SC Study Treatment (Year 1&2) | |
| 21.06. | 21.07 | ITT | Time to Belimumab SC Study Treatment Discontinuation [1] (Year 1&2) | |
| Protocol Deviations | | | | |
| 21.07. | 21.09 | ITT Year 2 | Important Protocol Deviations after Week 52 (Year 2) | 
 • Use new 'ITT Year 2' Population defined in Section 2.2. |
| Concomitant Medications | | | | |
| 21.08. | 21.11 | ITT Year 2 | Concomitant Medications by ATC Level 1 and ATC Level 4 Term (Year 2) | 
 • Use new 'ITT Year 2' Population defined in Section 2.2. |
| 21.09. | 21.13 | ITT | First Medication Usage Resulting in Treatment Failure Designation (Year 1&2) | |
| Extent of Exposure | | | | |
| 21.10. | 21.14 | ITT | Exposure to Belimumab SC (Study Treatment and Re-start [1]) (Year 1&2) | |

| Study Population Tables | | | | |
|---|-------------------|------------|--|--|
| New output number | Old output number | Population | Title | Major modifications since original RAP |
| 21.11. | 21.15 | ITT Year 2 | Exposure to Belimumab SC [1] (Arms A&B: Re-start; Arm C: Study Treatment) (Year 2) | 
 • Belimumab doses that occur up to and including the Week 52 visit date are included as Year 1 doses. Belimumab doses that occur after the Week 52 visit date are included as Year 2 doses. This was incorrect in the original RAP Section 6.5. • Use new 'ITT Year 2' Population defined in Section 2.2. |
| Coronavirus Disease 2019 (COVID-19) Pandemic | | | | |
| 21.12. | NEW | ITT | COVID-19 Pandemic Visit Impacts (Year 1&2) | 
 • New output (recommended in GSK COVID-19 guidance document) |

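### The Year 1&2 belimumab exposure table pools study treatment and re-start, with no stated duration rule that leaves out the treatment-free gap in Arms A and B

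*SAP*

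**What the plan says.** RAP Section 6.5 gives the rule as "Duration of exposure (days) = (Last injection date – First injection date + 7" and states that "First and last injection dates will be used, regardless of any missed doses". RAP Section 15.6.2 repeats it with no limit by arm or period.

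Section 6.5 sets the scope as "The extent of exposure to belimumab through Week 52 for Arm A and Arm B and through Week 104 for Arm C". It describes T21.14 for one arm only: "exposure to belimumab in Arm C from Baseline to Week 104 will also be summarized". Year 2 has its own summary, T21.15: "Exposure to belimumab will also be summarized for subjects during Year 2 only", counted from the first dose in that year. On the content of T21.15 it says: "For subjects in Arms A and B this will include incorrectly taken Year 1 medication after" Week 52, together with re-start doses.

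The July 2021 addendum, Section 2.1.1, renumbers T21.14 as Table 21.10 in the ITT population, titled "Exposure to Belimumab SC (Study Treatment and Re-start [1]) (Year 1&2"). Its modifications column is empty. The row for Table 21.11 (old T21.15) corrects Section 6.5 on which doses belong to Year 1 or Year 2, but not on how duration is computed.

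Under Protocol Section 5.1, Arms A and B are off study treatment in Weeks 53 to 104. Under Protocol Section 7.7.4, they "may continue or reinitiate open-label belimumab SC 200 mg weekly treatment" in that phase if certain conditions are met.

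**The concern.** A first-to-last span is a fair measure of exposure when dosing is planned to be continuous from the first injection to the last. It is not when the span contains a period in which the design withholds the drug. Table 21.10 appears to join two such periods for Arm A/B participants who re-start, and the only rule available makes no deduction for the interval between them.

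At stake is the accuracy of one descriptive column. A re-starter in Arm A or B could show the same duration as an Arm C participant dosed throughout, although the number of injections would differ widely.

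**Working it through.** **Inputs.** Weekly dosing from Day 1 through Week 51 in Arms A/B and through Week 103 in Arm C (Protocol Section 5.1). With week w falling on Day 1 + 7w, these last planned doses are Day 358 and Day 722. Duration = last − first + 7 (RAP 6.5, 15.6.2). The documents give no re-start dates or frequencies, so the re-start days below are assumptions.

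**1. The rule on planned continuous dosing.**
- Arms A/B: 358 − 1 + 7 = 364 days = 52 weeks.
- Arm C: 722 − 1 + 7 = 728 days = 104 weeks.

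Both match the treatment lengths in Protocol Section 7.3, so the rule works for the purpose Section 6.5 gives it.

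**2. The rule on pooled study treatment and re-start.** Take full Year 1 dosing, re-start on Day R and last re-start dose on Day L.
- Pooled span: L − 1 + 7 = L + 6.
- Sum of the two dosing periods: 364 + (L − R + 7).
- Excess: (L + 6) − (371 + L − R) = R − 365.

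The excess in days depends only on when re-start begins. The percentage also depends on L. With L = 722:

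| Re-start day R | Pooled span | Sum of periods | Excess | Excess as % of sum | Injections |
|---|---|---|---|---|---|
| 456 | 728 | 364 + 273 = 637 | 91 | 14% | 91 |
| 547 | 728 | 364 + 182 = 546 | 182 | 33% | 78 |
| 638 | 728 | 364 + 91 = 455 | 273 | 60% | 65 |

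A fully dosed Arm C participant also shows 728 days, with 104 injections.

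**3. The same participant under RAP 6.5 as written.** For R = 547, Year 1 gives 364 days and the Year 2 table gives 722 − 547 + 7 = 182 days. The gap between Week 52 and re-start is not counted. The problem therefore comes from the pooled table, not from Section 6.5 on its own.

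**4. The Year 2 table.** Suppose one late Year 1 dose on Day 372, re-start on Day 631 and dosing to Day 722. If late doses are kept in the table, the span is 722 − 372 + 7 = 357 days. The dosing is 7 + (722 − 631 + 7) = 105 days, so the excess is 252 days. With no late dose, the table gives 98 days and there is no excess.

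**The case against.** How Table 21.10 computes duration is inferred from its title. The text of its footnote [1] is not in the documents, and the mock shells are separate files (RAP Section 15.11.2). The table might show two durations, or the footnote might define one. This stands, and it makes the point conditional.

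The first-to-last span is also a declared convention that ignores missed doses in every arm, so duration never had to agree with the injection count. That is true of missed doses. A planned treatment-free phase is a different matter, and nothing in Section 6.5 suggests the convention was meant to span it.

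The title of Table 21.11 names only re-start for Arms A and B, which may exclude late Year 1 doses. Section 6.5 includes them, and the addendum's note assigns all doses after the Week 52 visit to Year 2. The text is ambiguous, so an error there is possible but not shown.

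Three stronger readings are tempting, and the documents do not support them:
- That RAP Section 6.5 itself counts the gap after Week 52. It does not: it handles Arms A/B through Week 52 and Year 2 separately.
- That Year 1&2 safety results are distorted. The exposure-adjusted rates use on-study time (RAP Sections 8.1.2 and 15.6.2). Injection counts, a separate Year 2 table and a listing of administrations (Listing 21.07) also remain.
- That arm averages are overstated by a known amount. This needs a re-start rate, re-start timing and time on re-start, none of which is given. Participants who continue belimumab straight after Week 52 would have almost no gap.

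**Conclusion.** The concern holds in a limited, conditional form. Table 21.10 pools study treatment and re-start. If the only stated duration rule is applied to it unchanged, the result for an Arm A/B re-starter is too long by the treatment-free interval. The illustrative excess of 91 to 273 days per re-starter assumes complete Year 1 dosing and the chosen re-start days; the 14% to 60% also assumes dosing to Day 722. In Table 21.11 the fault needs both a late Year 1 dose and a later re-start, with late doses kept in the table.

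No endpoint, hypothesis test or adverse event rate is touched. This is a minor clarification of a descriptive summary, worth making because the text as it stands leads a programmer to the wrong number.

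**What to change.** Add to the July 2021 addendum:
- **Table 21.10:** for Arms A and B, duration is the sum of the Year 1 period and the re-start period, each computed as last minus first plus 7. Alternatively, show the two durations on separate rows.
- **Table 21.11:** keep late Year 1 doses separate from re-start courses.

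Gaps from missed doses within a period stay under the present convention in all arms, so Arms A/B and Arm C are treated alike in that respect. If footnote [1] or the shell already contains such a rule, moving it into the addendum text is enough.

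The cost is a sentence or two and a small programming change. RAP Section 15.6.15.9 already adjudicates every Year 2 belimumab dose in Arms A and B as a late dose or a prescribed re-start, so no new data are needed.
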